3.2.2.2 Objective response rate

ORR is defined as the percentage of patients with a confirmed investigator-assessed response of CR or PR and will be based on all treated patients with measurable lesions at baseline.

A confirmed response of CR/PR means that a response of CR/PR is recorded at 1 visit and confirmed by repeat imaging no less than 4 weeks after the visit when the response was first observed with no evidence of progression between the initial and CR/PR confirmation visit. Data obtained up until progression, or last evaluable assessment in the absence of progression, will be included in the assessment of ORR. Patients who discontinue treatment without progression, receive a subsequent anticancer therapy (note that for this analysis radiotherapy is not considered a subsequent anticancer therapy) and then respond will not be included as responders in the ORR (ie, both visits contributing to a response must be prior to subsequent therapy for the patient to be considered as a responder).

In the case where a patient has 2 non-consecutive visit responses of PR, then, as long as the time between the 2 visits of PR is greater than 4 weeks and there is no PD between the PR visits, the patient will be defined as a responder. Similarly, if a patient has visit responses of CR, NE, CR, then, as long as the time between the 2 visits of CR is greater than 4 weeks, then a best response of CR will be assigned.

3.2.2.3 Duration of response

Duration of response (DoR) will be defined as the time from the date of first documented response (which is subsequently confirmed) until date of documented progression or death in the absence of disease progression (ie, date of PFS event or censoring – date of first response + 1). The end of response should coincide with the date of progression or death from any cause used

for the PFS endpoint. The time of the initial response will be defined as the latest of the dates contributing towards the first visit that was CR or PR that was subsequently confirmed. If a patient does not progress following a response, then their DoR will use the PFS censoring time.

3.2.2.4 Disease control rate

Disease control rate (DCR) is defined as the percentage of patients who have a best overall response of complete response or partial response or stable disease at ≥ 8 weeks. Patients must have lesions (either TLs or NTLs) recorded at baseline to be included in the denominator. The 8-week time point will allow for a visit window and be defined as on or after study day 49 (allowing for the visit window).

3.2.2.5 Time to treatment discontinuation or death (TTD)

Time to study treatment discontinuation or death (TTD) is defined as the time from first dose of osimertinib to the earlier of the date of study treatment discontinuation or death (ie, date of study treatment discontinuation/death or censoring – first dose of osimertinib + 1). Any patient not known to have discontinued treatment or not known to have died at the time of the analysis will be censored at the last known time to have not discontinued treatment, ie, the last follow-up visit where this was confirmed.

3.2.2.6 Time to first subsequent therapy or death (TFST)

The TFST will be defined as the time from the date of first dose of osimertinib to the earlier of the date of anticancer therapy start date following study treatment discontinuation, or death. Any patient not known to have had a subsequent therapy or not known to have died at the time of the analysis will be censored at the earlier of their last known to be alive date or study termination date.

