The TFST will be defined as the time from the date of first dose of osimertinib to the earlier of the date of anticancer therapy start date following study treatment discontinuation, or death. Any patient not known to have had a subsequent anticancer treatment or not known to have died at the time of the analysis will be censored at the last known time to have not received subsequent anticancer treatment, ie, the last follow-up visit where this was confirmed.

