9.3 Study Timetable and End of Study

A patient is considered to have completed the study when he/she has progressed or died.

The end of the study is defined as when the earliest of these scenarios is met:

- All enrolled patients complete their participation in the study either through disease progression or withdrawal for other reasons.
- The study will end in by Q2 2023, as it is estimated that by then there will be sufficient data to support study endpoints. If, at this time (Q2 2023 or at another time if AstraZeneca

or Regulatory Authorities decide to stop study due to any concerns, eg, patient safety), there are ongoing patients who are drawing benefit from study treatment, they will be switched to commercial supply and/or another study to ensure continuation of treatment, and the study will close using the available data for the final analysis. A CSR will be written at this time, including all data collected during the study.

For any patients who continue in progression follow-up, any additional safety data will be collected and summarised in the CSR.

The study may be terminated at individual centres if the study procedures are not being performed according to GCP, or if recruitment is slow. AstraZeneca may also terminate the entire study prematurely if concerns for safety arise within this study or in any other study with osimertinib.

The study may be terminated at individual centres if there are no ongoing patients.

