3.2.2.1 Progression-free survival

PFS is defined as the time from the first dose of osimertinib until the date of RECIST 1.1-defined progression or death (by any cause in the absence of progression) regardless of whether the patient withdraws from therapy or receives another anticancer therapy prior to progression. PFS is calculated in months as follows:

$$PFS = \frac{\text{date of objective disease progression or censoring} - \text{date of first dose of osimertinib} + 1}{30.4375}$$

Patients who have not progressed or died at the date of analysis will be censored at the time of the latest date of assessment from their last evaluable RECIST 1.1 assessment.

However, if the patient progresses or dies after two or more missed visits (126 days), the patient will be censored at the time of the latest evaluable RECIST 1.1 assessment.

Given the scheduled visit assessment scheme (i.e., eight-weekly for the first 3.5 years [D1277] then ten-weekly thereafter) the definition of 2 missed visits will change. Due to a delay in enacting CSP version 5.0 there was some variability in when patients transitioned to 10-weekly visit. However, we will apply the following rules to all patients.

1. If the previous RECIST 1.1 assessment is baseline, then two missing visits will equate to 17 weeks since the previous RECIST 1.1 assessment, allowing for a late visit (i.e., 2×8 weeks + 1 week for a late assessment = 17 weeks [119 days]).
2. If the previous RECIST 1.1 assessment is post baseline and \leq study day 1169, then two missing visits will equate to 18 weeks since the previous RECIST 1.1 assessment, allowing for early and late visits (i.e., 2×8 weeks + 1 week for an early assessment + 1 week for a late assessment = 18 weeks [126 days]).
3. If the previous RECIST 1.1 assessment study day is > 1169 and ≤ 1225 , then the two missed visits occur over the period when the scheduled frequency of RECIST 1.1 assessments changes from eight-weekly to ten-weekly, then this will equate to 21 weeks (i.e., take the average of 8 and 10 weeks which gives 9 weeks and then apply same rationale, hence 2×9 weeks + 1 week for an early assessment + 2 week for a late assessment = 21 weeks [147 days]).
4. If the previous RECIST 1.1 assessment study day is > 1225 (when the scheduling changes to ten-weekly assessments), two missing visits will equate to 24 weeks (i.e., 2×10 weeks + 2 week for an early assessment + 2 week for a late assessment = 24 weeks [168 days]).

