3.3.2.1 Imputation of partial dates

Concomitant medication and adverse events start dates

- If year is missing (or completely missing), do not impute.
- If (year is present and month and day are missing) or (year and day are present and month is missing), impute as January 1st.
- If year and month are present and day is missing, impute day as first day of the month.

Concomitant medication and adverse events end dates

- If year is missing (or completely missing), do not impute.
- If (year is present and month and day are missing) or (year and day are present and month is missing), impute as December 31st, unless this is after the date of death in which case date of death will be used instead.
- If year and month are present and day is missing, impute day as last day of the month, unless this is after the date of death in which case date of death will be used instead.

In addition, for AEs and CMs if, for a partial start date, the start date could (when also considering the end date) potentially be on the first study medication date, the start date will be imputed with the first study medication date to assume a “worst case” scenario; eg, AE from UNK-Feb-2014 to 23-Mar-2014 with first study medication date 21-Feb-2014, then the AE start date will be imputed to 21-Feb-2014.

If a patient is known to have died where only a partial death date is available then the date of death will be imputed as the latest of the last date known to be alive +1 from the database and the death date using the available information provided:

- For Missing day only – using the 1st of the month

- For Missing day and Month – using the 1st of January

If there is evidence of death but the date is entirely missing, it will be treated as missing, ie, censored at the last known alive date.

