6. CHANGES OF ANALYSIS FROM PROTOCOL

Version 7.0 of the protocol was used when writing the statistical analysis plan.

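### SAP 3.2.2.6 censors time to first subsequent therapy on being alive, capped by an undefined study termination date; Protocol 8.4.2 censors at the last visit confirming no such therapy, and SAP Section 6 lists no change

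*SAP*

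**What the plan says.** Protocol 8.4.2 and SAP 3.2.2.6 give TFST the same start (first dose of osimertinib) and the same event (start of anticancer therapy after stopping study treatment, or death). They differ in how a patient without an event is censored.

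- Protocol 8.4.2: "censored at the last known time to have not received subsequent anticancer treatment, ie, the last follow-up visit where this was confirmed".
- SAP 3.2.2.6: "censored at the earlier of their last known to be alive date or study termination date".

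The SAP's other time-to-event endpoints are tied to an assessment of the event concerned:

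- PFS (3.2.2.1): "censored at the time of the latest date of assessment from their last evaluable RECIST 1.1 assessment".
- Duration of response (3.2.2.3): "If a patient does not progress following a response, then their DoR will use the PFS censoring time".
- Time to treatment discontinuation or death, TTD (3.2.2.5): "censored at the last known time to have not discontinued treatment, ie, the last follow-up visit where this was confirmed".

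SAP Section 6, which is meant to list changes from the protocol, contains one sentence: "Version 7.0 of the protocol was used when writing the statistical analysis plan". The SAP amendment history has an entry of 17 September 2021 for a section then numbered 3.1.2.2.6, saying that censoring rules were clarified. It is marked as in line with the protocol, on the ground that the protocol does not go into that detail.

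**The concern.** TFST asks whether a new therapy has started. Evidence that a patient is alive does not answer that, so a last-alive date can run past the point up to which therapy status is known. The patient then stays in the risk set as event-free over time that nobody checked.

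The second difficulty is *study termination date*. The term appears only in SAP 3.2.2.6, and since the rule takes the earlier of two dates, its meaning decides when the cap applies. Two programmers could derive different TFST values from the same data.

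TFST and TTD are the two outcomes of the post-progression objective (Protocol 2.2). The protocol gives both the same type of rule, and the SAP keeps it for TTD only. At stake is whether a protocol-defined secondary endpoint can be reproduced and traced. No hypothesis test or primary result depends on it.

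**Working it through.** **Step 1. What the undefined date could mean.** The documents allow at least four readings:

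| Reading | Effect relative to Protocol 8.4.2 |
|---|---|
| The patient's own study exit | Close to the protocol rule if the patient is followed to first subsequent therapy or death, as Protocol 4.3 and Table 2 (footnote m) provide |
| Completion at progression (Protocol 9.3: "A patient is considered to have completed the study when he/she has progressed or died") | Can censor earlier and lose confirmed therapy-free time, such as the 28-day contact (4.3.1) or treatment beyond progression (4.2) |
| Final data cut-off (SAP 1.2) | Cap rarely applies; in practice the last-alive date |
| Study-level end (Protocol 9.3, 9.3.1) | As for the data cut-off |

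The direction of the effect therefore depends on a definition that is not given.

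**Step 2. One patient, with assumed dates.** Last visit confirming no new therapy: study Day 600. Last known alive: Day 900. Study-level end: later. Using the SAP's 30.4375 days per month:

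- Protocol rule: 600 / 30.4375 = 19.7 months.
- SAP rule: 900 / 30.4375 = 29.6 months.
- Unconfirmed event-free time: 300 / 30.4375 = 9.9 months.

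The difference is simply the gap between the two dates. It is 0 if they coincide and 56 / 30.4375 = 1.8 months for an 8-week gap.

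**Step 3. Effect on the median, with assumed inputs.** The documents supply only the exponential progression time with a 19-month median (Protocol 8.1). I assumed that drug stops at progression, that the next therapy starts after an exponential time with mean 1.5 months, and that follow-up is uniform over 48 to 60 months. A given share of patients have unknown therapy status after their last check, then stay known alive for an exponential further time. With 2,000,000 simulated patients the true median TFST is about 20.5 months. On the study-level reading:

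| Last check | Share unknown | Protocol rule minus truth (months) | SAP minus protocol rule, mean gap 3 months | Same, mean gap 12 months |
|---|---|---|---|---|
| At progression | 5% | +0.9 | +0.10 | +0.29 |
| At progression | 10% | +2.0 | +0.22 | +0.64 |
| At progression | 20% | +4.5 | +0.49 | +1.55 |
| 28 days later | 5% | +0.5 | +0.05 | +0.15 |
| 28 days later | 10% | +1.0 | +0.11 | +0.31 |
| 28 days later | 20% | +2.1 | +0.23 | +0.68 |

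A mean gap of 0 gives no difference. On the progression reading with a 28-day check the sign reverses, at -0.02 to -0.08 months. It reaches -0.45 months if half the patients continue drug for a mean of 6 months beyond progression. For comparison, the sampling range of the median with 150 patients in this model is about 16 to 25 months.

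**Step 4. Which end of the range is plausible.** Current Protocol 3.8 asks for no vital-status check and there is no survival endpoint. The 28-day contact and the progression follow-up both ask about subsequent therapy (4.3.1, 4.3.2, Table 2). The last-alive date and the last therapy check should then usually be the same day, which puts the effect near zero.

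**The case against.** The strongest reply has four parts.

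- **The change was logged.** The entry following the one for old Section 3.1.2.2.6 concerns best change in target lesion size, now 3.2.2.7, so the entry is very probably the TFST rule. A reader might infer a silent departure; the log does not support that. What stands is that it is recorded as compatible detail, although Protocol 7.0, which the SAP says it follows, states a different rule.
- **Last-alive censoring is not unique to TFST.** A reader might infer that TFST alone uses it. SAP 3.3.2.1 also censors at the last known alive date when a death is evident but its date is wholly missing, and names no endpoint. The same section's "latest of the last date known to be alive +1 from the database" concerns partial death dates, so it does not show that last-alive dates come from contacts where therapy went unchecked.
- **The SAP rule does not always overstate TFST.** Extra follow-up moves the curve only if another patient's event falls between the two dates, and moves the median only if the gap begins before it. Patients still on osimertinib cannot yet have a subsequent-therapy event. The accurate statement is that the rule can overstate.
- **The protocol rule leaves a larger error.** In the table above, therapy starts that were never captured bias the protocol rule by more than the SAP rule adds. That is correct: restoring the protocol rule removes the added part and does not recover missing starts.

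Different censoring for TTD and TFST is also not an error in itself, since the events differ. None of this removes the contradiction or supplies the missing definition.

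**Conclusion.** The point holds as a minor inconsistency. SAP 3.2.2.6 replaces confirmed absence of therapy with vital status, caps it with an undefined date, and is not listed in SAP Section 6. The possible bias is upward where the last-alive date is later than the last therapy check, and downward if the cap means progression.

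The documents give neither the share of patients with unknown status nor the gaps, so the size cannot be derived from them. Every simulated value rests on assumed inputs and serves only to show scale. The likely effect is near zero, and even the larger scenarios are small against sampling error with 150 patients. TFST is summarised by Kaplan-Meier methods without a test (SAP 4.2.9.7), and the primary analysis is untouched. A reader might infer a materially biased efficacy result; the documents do not support that.

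**What to change.** In SAP 3.2.2.6, censor TFST at the last date on which absence of subsequent anticancer treatment was confirmed, as in Protocol 8.4.2, and delete *study termination date*. If last-alive censoring is kept, make it a sensitivity analysis, define its cap as a specific date, and list it in SAP Section 6. A short table giving the number of censored patients whose last-alive date is later than their last therapy check, with the length of the gap, would show the actual size.

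The cost is one SAP sentence, one line in Section 6 if the alternative is kept, and one small table. No new data are needed.

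A separate point for the sponsor is how long subsequent therapy is captured. Protocol 3.6.1 and 9.3 tie capture or completion to progression, while the synopsis, Section 4.3 and Table 2 (footnote m) follow patients to first subsequent therapy or death. These passages should be reconciled, because changing the censoring rule cannot make up for therapy starts that were not recorded.

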3.2.2.7 Best percentage change in TL tumour size

The percentage change from baseline in TL tumour size will be calculated every 8 weeks. This is based on RECIST TL measurements taken at baseline. Tumour size is the sum of the longest diameters of the TLs. TLs are measurable tumour lesions. Baseline is defined as in Section [3.1.1](#). The percentage change in TL tumour size is calculated by

$$\frac{TL \text{ tumour size} - \text{baseline TL tumour size}}{\text{baseline TL tumour size}} \times 100\%.$$

The best percentage change in TL size is the maximum reduction from baseline or the minimum increase from baseline in the absence of a reduction over the course of the study and will include all assessments prior to the earliest of death in the absence of progression, any evidence of

progression, the start of subsequent anticancer therapy. A negative change denotes a reduction in target lesion size.

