2.2 Secondary Objectives

Secondary Objectives:	Outcome Measures:
To assess the efficacy of osimertinib as first-line EGFR TKI therapy for patients with EGFRm+ locally advanced or metastatic NSCLC	PFS, according to RECIST 1.1 by Investigator assessment, and other selected clinical efficacy endpoints including: 
• ORR• DoR• DCR
To assess the efficacy of osimertinib in patient subgroups defined by molecular profile, including but not limited to: 
• EGFR Ex19del or L858R mutation• EGFR Ex19del or L858R detectable in plasma-derived circulating tumour deoxyribonucleic acid (ctDNA)	PFS, according to RECIST 1.1 by Investigator assessment, and other selected clinical efficacy endpoints including: 
• ORR• Tumour shrinkage/depth of response, defined as best change from baseline in target lesion tumour size• Time to treatment discontinuation or death (TTD)• Important patient and disease characteristics
To further assess the efficacy of osimertinib post-progression	
• TTD• Time to first subsequent therapy or death (TFST)

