2.1.2 Full analysis set

The (FAS) will include all patients who receive at least one dose of osimertinib. The FAS will be used for all efficacy and safety analyses.

[Table 3](#) summarises the population analysis sets for each outcome variable.

Table 3 Summary of outcome variables and analysis populations

Outcome variable	Population
Primary objective	
Proportion of patients with a given marker at progression as defined by the investigator	PAS
Efficacy data	
PFS, ORR, DoR, DCR, TTD, TFST	FAS
Subgroup analysis	
PFS, ORR, Best change in TL tumour size, TTD	FAS
Important patient and disease characteristics	FAS, PAS
Demography data	
Important patient and disease characteristics	FAS, PAS
Safety data	
Exposure	FAS
AEs	FAS
Laboratory measurements	FAS
Vital signs	FAS
Physical examinations	FAS
Electrocardiograms (ECGs)	FAS

Abbreviations: AEs = Adverse events; DCR = Disease control rate; DoR = Duration of response; ECG = Electrocardiogram; FAS = Full analysis set; ORR = Objective response rate; PAS = Primary analysis set; PFS = Progression free survival; TFST = Time to first subsequent therapy or death; TL = Target lesion; TTD = Time to treatment discontinuation or death.

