3. PRIMARY AND SECONDARY VARIABLES

3.1 Efficacy

3.1.1 Derivation of RECIST visit responses

For all patients, the RECIST tumour response data will be used to determine each patient’s visit response according to RECIST version 1.1. It will also be used to determine if, and when, a patient has progressed in accordance with RECIST and their best objective response to study drug.

Baseline radiological tumour assessments are to be performed no more than 28 days before the first dose of treatment, and as close as possible to the start of study treatment. Assessments on the day of the first dose where neither time nor a nominal pre-dose indicator are captured will be considered prior to the first dose if such procedures are required by the protocol to be conducted before the first dose. Tumour assessments are then performed every 8 weeks (± 1 week) following the start of study treatment until objective disease progression.

If an unscheduled assessment is performed, and the patient has not progressed, every attempt should be made to perform the subsequent assessments at their scheduled visits. This schedule is to be followed to minimise any unintentional bias caused by some patients being assessed at a different frequency than other patients.

From the Investigator's review of the imaging scans, the RECIST tumour response data will be used to determine each patient's visit response according to RECIST 1.1. At each visit, patients will be programmatically assigned a RECIST 1.1 visit response of complete response (CR), partial response (PR), stable disease (SD) or progressive disease (PD), using the information from target lesions (TLs), non-target lesions (NTLs) and new lesions and depending on the status of their disease compared with baseline and previous assessments. If a patient has had a tumour assessment that cannot be evaluated then the patient will be assigned a visit response of not evaluable (NE), (unless there is evidence of progression in which case the response will be assigned as PD).

Please refer to [Table 4](#) for the definitions of CR, PR, SD, and PD.

RECIST outcomes (ie, PFS, ORR etc.) will be calculated programmatically for the site Investigator data (see [Section 3.2](#)) from the overall visit responses.

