3.3.2 Handling missing data

In general, other than for partial dates, missing data will not be imputed and will be treated as missing with the exceptions specified for certain efficacy variables.

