4.3.1 Best change in TL tumour size

The best change in TL tumour size from baseline, (where best change in TL size is the maximum reduction from baseline or the minimum increase from baseline in the absence of a reduction) up until RECIST 1.1 progression will also be summarised for each subgroup.

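### Read literally, SAP 3.2.2.7 leaves out the scan that shows progression, so first-scan progressors have no best-change value in the Ex19del and L858R summaries; SAP 4.3.1 does not settle the point

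*SAP*

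**What the plan says.** Protocol 2.2 lists, as an outcome in the molecular subgroups, "Tumour shrinkage/depth of response, defined as best change from baseline in target lesion tumour size". It sets no progression cut-off.

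SAP 3.2.2.7 takes the largest reduction from baseline or, if there is none, the smallest increase. It then limits the scans that count. The variable "will include all assessments prior to the earliest of death in the absence of progression", any evidence of "progression, the start of subsequent anticancer therapy" (one sentence, split over a page break).

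SAP 4.3.1, which describes the summary itself, says that the best change "up until RECIST 1.1 progression will also be summarised for each subgroup". The subgroups in SAP 4.3 are EGFR Ex19del and L858R, each analysed only if it has at least 20 progression events.

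SAP Table 3 assigns "PFS, ORR, Best change in TL tumour size, TTD" to the full analysis set. SAP 3.3.2 says that, apart from partial dates, "missing data will not be imputed and will be treated as missing with the exceptions specified for certain efficacy variables". SAP 3.2.2.7 specifies no exception. On timing, SAP 3.1.1 says "Tumour assessments are then performed every 8 weeks", with a one-week window.

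**The concern.** If only scans before any evidence of progression count, a patient who progresses at the first post-baseline scan has no eligible scan. The exclusion depends on the outcome. These patients should on average show the least shrinkage, so their absence should make the subgroup summaries look somewhat better than they are.

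The rule also conflicts with the definition it belongs to, which provides for patients whose lesions only grow but then removes most of the scans that would show substantial growth.

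The two SAP sections can also be programmed differently. SAP 4.3.1 refers to RECIST 1.1 progression where 3.2.2.7 refers to any evidence of progression, and it omits the subsequent-therapy cut-off. Protocol 5.1.1 continues scans after other anticancer treatment until progression, so that omission can change a patient's value.

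**Working it through.** **1. Which patients lose their value.** Take a patient with a baseline scan and one post-baseline scan, which shows progression.

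- SAP 3.2.2.7, read literally: no scan precedes the evidence of progression, so there is no value.
- SAP 3.3.2: no imputation, so the value stays missing.
- SAP 4.3.1: the value is kept if its limit includes the progression scan and lost if it does not. The wording allows either.
- Protocol 2.2: the scan would count.

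**2. What the rule cuts off.** If target lesions never shrink, the smallest sum on study is the baseline sum. SAP Table 4 defines target-lesion progression as a rise of at least 20% and at least 5 mm over that smallest sum. Since 20% of 25 mm is 5 mm, any rise of 20% or more from a baseline sum of 25 mm or more is progression and is excluded. With smaller baseline sums, a rise of 20% or more can survive only if it is under 5 mm.

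**3. How many patients.** The documents give no rate of progression at the first scan. Two proxies are available.

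- *Cited disease control.* Protocol 1.1 reports a DCR of 98% (95% CI 89% to 100%) in 60 first-line patients, half of them on 160 mg. The complement is about 2%, or 0.02 x 150 = 3 patients study-wide. The lower confidence limit gives 11%.
- *The planning model.* SAP 1.3 assumes exponential progression times with a 19-month median. To reproduce the plan's own figure, put 100 patients uniformly over months 0 to 5 and 50 over months 11 to 12 (protocol 8.1; uniform entry is a simplification). With rate ln 2 / 19 = 0.03648 per month, expected events at month 38 are 72.6 + 31.0 = 103.6, against the stated 103. The same rate gives 1 - exp(-0.03648 x 56/30.4375) = 6.5% with an event by day 56, or about 9.7 of 150. Over days 49 to 63 the range is 5.7% to 7.3%. Deaths are included.

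These counts are ceilings for the affected output, which covers only the two subgroups and only patients with baseline target lesions.

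**4. Effect on the mean.** Let f be the share dropped. The mean over everyone is (1 - f) x (retained mean) + f x (dropped mean), so dropping them shifts the mean by f x (dropped mean - retained mean). Assumption, not in the documents: the retained mean is -50%.

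| Share f | Dropped at -20% | Dropped at +20% | Dropped at +30% |
|---|---|---|---|
| 2% | 0.02 x 30 = 0.6 | 0.02 x 70 = 1.4 | 0.02 x 80 = 1.6 |
| 6.5% | 0.065 x 30 = 1.95 | 0.065 x 70 = 4.55 | 0.065 x 80 = 5.2 |
| 11% (outer bound) | 3.3 | 7.7 | 8.8 |

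Entries are percentage points by which mean shrinkage looks too deep. The -20% column represents progression by new or non-target lesions while target lesions shrink.

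**5. Effect on the median.** A simulation with a retained SD of 25 points (also an assumption) shifts the median by about 0.6 points at 2% and 2.2 points at 6.5%.

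**The case against.** The strongest reply is that only one reading of the text drops anyone. If SAP 4.3.1 is inclusive, the section that governs the summary keeps the progression scan. That stands as a reason to call the SAP unsettled. It does not rescue 3.2.2.7, which defines the variable and excludes the scan on its face.

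A reader might infer that the worst responders are removed as a class. The documents do not support that. Under SAP 3.1.1.2 a new lesion or non-target progression gives progressive disease whatever the target lesions do, so some dropped patients may have shrinking target lesions. For them the bias is smaller, and it is nil if they resemble the rest.

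The rates are weak. The DCR comes from a small cohort at mixed doses. The 6.5% includes deaths, and a patient who dies before any scan has no value under either rule. Reproducing 103 events at 38 months says nothing specific about the hazard in the first eight weeks.

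Counting the progression scan also affects later progressors. Adding a scan to a minimum can only deepen the best change or leave it unchanged, for example when a new lesion appears while target lesions are at their smallest. The net effect of the correction is therefore somewhat smaller than the table shows.

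Finally, first-scan progressors remain visible elsewhere: as PFS events and, if they had measurable lesions, as ORR non-responders in the same subgroups. SAP 4.1 reports the number of observations, so a shortfall would show, but without its reason.

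**Conclusion.** The point holds as a wording defect with a small, outcome-dependent effect. As written, SAP 3.2.2.7 gives first-scan progressors no value, and SAP 4.3.1 neither resolves this nor repeats the subsequent-therapy cut-off.

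The expected direction is a modest overstatement of shrinkage: about 0.6 to 5 points on the mean. This rests on an assumed first-scan progression share of 2% to 6.5%, a retained mean of -50% and a dropped mean between -20% and +30%. Where progression is by new or non-target lesions, the -20% column (0.6 to about 2 points) is the better guide.

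It would be tempting to state a fixed overstatement of several points across all 150 patients. The documents do not support that: they give no rate and no distribution of best change, and the output covers only two subgroups. It is a descriptive summary with no test or decision attached. The primary endpoint, PFS, ORR and DCR do not depend on this rule.

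**What to change.** Use the same sentence in SAP 3.2.2.7 and 4.3.1: best change includes all assessments with measured target lesions up to and including the first assessment showing progression, and before the start of subsequent anticancer therapy.

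In each subgroup summary, add the number of patients with baseline target lesions who have no eligible post-baseline value, with the reason (for example death before a scan, no scan, or target lesions not measured).

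The cost is one SAP phrase, one programming condition and one extra table row. No new data are needed, because scans are already collected up to progression. The slight deepening for some later progressors is a small price for a rule that no longer excludes patients by outcome.
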